### 8.2.3 Imputation Analyses for primary endpoints on mITT analysis set

If more than 10% of participants in the mITT analysis have one or more of the meningitis serogroup endpoints missing, an imputation analysis will be conducted in addition to a complete case analysis. Separate imputation analyses will be done for Group 1 and in Group 2.

#### Step 2 – Imputation:

Imputation of rSBA levels will be conducted using MI Procedure in SAS. Depending on the type of missing pattern, either a monotone regression method (for a monotone pattern of missingness) or fully conditional (FCS) method (for an arbitrary pattern of missingness) will be used. All variables identified in the model specification step will be included. A total of 25 complete datasets with imputed outcomes will be produced.

#### Step 3 - Analysis and combining results:

After imputation, complete imputed datasets will be analyzed, as specified in Section 8.2.1 and 8.2.2, to obtain the relevant test statistics. The MIANALYZE Procedure in SAS will be used to obtain point and interval estimates of relevant test statistics, which incorporate within-imputation and between-imputation variance. Results will be presented as described for the results of the main analysis.

## 8.3 Secondary Immunogenicity Analyses

Objectives:

- To demonstrate that the immune responses to meningococcal serogroup X elicited by one dose of NmCV-5 (at either 9 or 15 months of age) is superior to that elicited by MenACWY-TT (at either 9 or 15 months of age) measured by rSBA titers at 28 days after vaccination.
- To demonstrate the non-inferiority of the immune responses to EPI vaccines (measles-rubella, yellow fever, measles booster) when co-administered with NmCV5 (at either 9 or 15 months of

age) compared to the immune responses when co-administered with MenACWY-TT (at either 9 or 15 months).

- To assess clinically significant immune response indicators elicited by a single dose of NmCV-5, given concomitantly with routine vaccines, as compared to those elicited by MenACWY-TT.

### 8.3.1 Superiority immune responses to meningococcal serogroup X

**Hypothesis:** Null hypothesis: The immune response to meningitis serogroup X at Day 29 elicited by one dose of NmCV-5 is not superior to the immune response elicited by one dose of MenACWY-TT,

Alternative hypothesis: The immune response to meningitis serogroup X at Day 29 elicited by one dose of NmCV-5 is superior, by a pre-specified margin, to the immune response elicited by one dose of MenACWY-TT.

**Endpoints:**

- Seroprotective response to serogroup X in the NmCV-5 arm at Day 29,
- seroprotective response to serogroup X MenACWY-TT arm at Day 29,

with seroprotective response is defined as rSBA antibody titers  $\geq 8$ .

**Strata:** Age group (from Step 2 randomization): Group 1 (9-12 months) and Group 2 (15-18 months of age).

**Analysis Set(s):** The primary analysis will be conducted on the Per Protocol (PP) Analysis Set, with a secondary analysis conducted on the Meningitis mITT Analysis Set.

**Approach:** The proportion of infants (randomized to NmCV-5 vs. MenACWY-TT) with a seroprotective response to serogroup X will be calculated as

$$p_{V,X} = \frac{\sum_{i=1}^{N_V} I(Y_i^{V,X} \geq 8)}{N_V} = \frac{n_{V,X}}{N_V},$$

where V indicates arm (NmCV-5 vs. MenACWY-TT), X indicates serogroup X,  $N_V$  is the number of infants in the analysis set randomized to arm V and  $Y_i^{V,X}$  is the rSBA antibody titer to serogroup X for the  $i^{\text{th}}$  infant in arm V.

NmCV-5 will be deemed superior to MenACWY-TT for eliciting a seroprotective response to serogroup X, by at least 30%, if the lower limit of the 95% confidence interval for  $p_{NmCV-5,X} - p_{MenACWY-TT,X}$  excludes 0.30.

Confidence Intervals will be calculated using the Miettinen-Nurminen method [1, 2].

**Reporting:** The number ( $n_{V,X}$ ) and proportion ( $p_{V,X}$ ) of participants with seroprotective response will be provided (by arm), along with point and 95% CI estimates of the difference in proportions ( $p_{NmCV-5,X} - p_{MenACWY-TT,X}$ ).

**Graphical display:** None

### 8.3.2 Non-inferiority of the seropositive response to Measles vaccine

**Hypothesis:** Null hypothesis: The immune response to measles at Day 29 elicited by the MR vaccine when co-administered with one dose of NmCV-5 is inferior to the immune response elicited by the MR vaccine when co-administered with one dose of MenACWY-TT,

Alternative hypothesis: The immune response to measles at Day 29 elicited by the MR vaccine when co-administered with one dose of NmCV-5 is non inferior, by a pre-specified margin, to the immune response elicited by the MR vaccine when co-administered with one dose of MenACWY-TT.

- Endpoints:** Seropositive response to measles vaccine at Day 29 post vaccination, defined as anti-measles IgG concentration >200 mIU/ml.
- Strata:** Meningitis vaccination age group: Group 1 (9-12 months) and Group 2 (15-18 months of age).
- Analysis Set(s):** Per Protocol (PP) Analysis Set.
- Approach:** The proportion of infants with a seropositive response to measles vaccine at Day 29 will be calculated as:

$$p_V^{Measles} = \frac{\sum_{i=1}^{N_V} I(M_i^V > 200)}{N_V} = \frac{n_V^{Measles}}{N_V},$$

where V indicates arm (NmCV-5 vs. MenACWY-TT),  $N_V$  is the number of infants in the analysis set randomized to arm V and  $M_i^V$  is the anti-measles IgG concentration (in mIU/ml) at Day 29 for  $i^{\text{th}}$  infant in arm V.

The NmCV-5 co-administered MR vaccine will be deemed non-inferior to the MenACWY-TT co-administered MR vaccine in eliciting seropositive response to measles if the lower limit of the 95% confidence interval for  $p_{NmCV-5}^{Measles} - p_{MenACWY-TT}^{Measles}$  excludes -0.10.

Confidence Intervals will be calculated using the Miettinen-Nurminen method [1, 2].

- Reporting:** The number ( $n_V^{Measles}$ ) and proportion ( $p_V^{Measles}$ ) of participants with seropositive response to measles will be provided (by arm), along with point and 95% CI estimates of the difference in proportions ( $p_{NmCV-5}^{Measles} - p_{MenACWY-TT}^{Measles}$ ). Proportions and difference in proportions will be reported as percentages (number of infants per 100), with one decimal place.
- Graphical display:** Point estimates and 95% CIs for  $p_{NmCV-5}^{Measles} - p_{MenACWY-TT}^{Measles}$  will be displayed graphically in a forest plot, with the non-inferiority margin (expressed as -10%) included as reference.

### 8.3.3 Non-inferiority of the seropositive response to Rubella vaccine

- Hypothesis:** Null hypothesis: The immune response to rubella at Day 29 elicited by the MR vaccine when co-administered with one dose of NmCV-5 is inferior to the immune response elicited by the MR vaccine when co-administered with one dose of MenACWY-TT, Alternative hypothesis: The immune response to rubella at Day 29 elicited by the MR vaccine when co-administered with one dose of NmCV-5 is non inferior, by a pre-specified margin, to the immune response elicited by the MR vaccine when co-administered with one dose of MenACWY-TT,
- Endpoints:** Seropositive response to rubella vaccine at Day 29 post vaccination, defined as anti-rubella IgG concentration > 20 IU/ml.
- Strata:** Meningitis vaccination age group: Group 1 (9-12 months) and Group 2 (15-18 months of age).

Analysis Set(s): Per Protocol (PP) Analysis Set.

Approach: The proportion of infants with a seropositive response to measles vaccine at Day 29 will be calculated as:

$$p_V^{Rubella} = \frac{\sum_{i=1}^{N_V} I(R_i^V > 20)}{N_V} = \frac{n_V^{Rubella}}{N_V},$$

where V indicates arm (NmCV-5 vs. MenACWY-TT),  $N_V$  is the number of infants in the analysis set randomized to arm V and  $R_i^V$  is the anti-rubella IgG concentration (in IU/ml) at Day 29 for  $i^{\text{th}}$  infant in arm V.

The NmCV-5 co-administered MR vaccine will be deemed non-inferior to the MenACWY-TT co-administered MR vaccine in eliciting seropositive response to rubella if the lower limit of the 95% confidence interval for  $p_{NmCV-5}^{Rubella} - p_{MenACWY-TT}^{Rubella}$  excludes -0.10.

Confidence Intervals will be calculated using the Miettinen-Nurminen method [1, 2].

Reporting: The number ( $n_V^{Rubella}$ ) and proportion ( $p_V^{Rubella}$ ) of participants with seropositive response to rubella will be provided (by arm), along with point and 95% CI estimates of the difference in proportions ( $p_{NmCV-5}^{Rubella} - p_{MenACWY-TT}^{Rubella}$ ).

Graphical display: Point estimates and 95% CIs for  $p_{NmCV-5}^{Rubella} - p_{MenACWY-TT}^{Rubella}$  will be displayed graphically in a forest plot, with the non-inferiority margin (expressed as -10%) included as reference.

### 8.3.4 Non inferiority of the seroprotective response to yellow fever vaccine

Hypothesis: Null hypothesis: The immune response to yellow fever at Day 29 elicited by the yellow fever vaccine when co-administered with one dose of NmCV-5 is inferior to the immune response elicited by the yellow fever vaccine when co-administered with one dose of MenACWY-TT.

Alternative hypothesis: The immune response to yellow fever at Day 29 elicited by the yellow fever vaccine when co-administered with one dose of NmCV-5 is non inferior, by a pre-specified margin, to the immune response elicited by the yellow fever vaccine when co-administered with one dose of MenACWY-TT.

Endpoints: Seroprotective response to yellow fever vaccine at Day 29 post vaccination, defined as yellow fever neutralizing antibody titers  $\geq 10$ .

Strata: Not applicable for this endpoint.

Analysis Set(s): Per Protocol (PP) Analysis Set (defined in Group 1 only).

Approach: The proportion of infants with a seroprotective response to yellow fever vaccine at Day 29 will be calculated as:

$$p_V^{YF} = \frac{\sum_{i=1}^{N_V} I(F_i^V \geq 10)}{N_V} = \frac{n_V^{YF}}{N_V},$$

where V indicates arm (NmCV-5 vs. MenACWY-TT),  $N_V$  is the number of infants in the analysis set randomized to arm V and  $F_i^V$  is the yellow fever neutralizing antibody titers at Day 29 for  $i^{\text{th}}$  infant in arm V.

The NmCV-5 co-administered YF vaccine will be deemed non-inferior to the MenACWY-TT co-administered YF vaccine in eliciting seroprotective response to

yellow fever if the lower limit of the 95% confidence interval for  $p_{NmCV-5}^{YF} - p_{MenACWY-TT}^{YF}$  excludes -0.10.

Confidence Intervals will be calculated using the Miettinen-Nurminen method [1, 2].

Reporting:	The number ( $n_V^{YF}$ ) and proportion ( $p_V$ ) of participants with seroprotective response will be provided (by arm), along with point and 95% CI estimates of the difference in proportions ( $p_{NmCV-5}^{YF} - p_{MenACWY-TT}^{YF}$ ).
Graphical display:	Point estimates and 95% CIs for $p_{NmCV-5}^{YF} - p_{MenACWY-TT}^{YF}$ will be displayed graphically in a forest plot, with the non-inferiority margin (expressed as -10%) included as reference.

### 8.3.5 Level of rSBA titers and seroresponse at Day 29

A descriptive analysis of the distribution of rSBA titers at Day 29 will be conducted, as follows:

Endpoint:	rSBA titers against meningococcal serogroups A, C, W, X and Y, from samples collected at Visit 3 (Study Day 29).
Analysis Set:	Per Protocol (PP) Analysis Set and the Baseline Immunogenicity Analysis Set
Approach and reporting:	For each of the five serogroups (A, C, W, X, Y), the Geometric Mean Titer (GMT) Ratio of rSBA titers at Day 29 for NmCV-5 relative to MenACWY-TT will be estimated, along with 95% CIs. The point and interval estimates will be obtained from a back transformation of the estimated difference in means of the log-transformed rSBA titers. This analysis will only apply to the Per Protocol Analysis Set.  For each of the five serogroups (A, C, W, X, Y), descriptive summaries for rSBA titers at Day 29 will be tabulated by arm. These will include: 
 
- Geometric Mean Titers (GMT), with 95% confidence intervals.
 
- Range.
 
- Number and percentage of participants with rSBA titers <math>\geq 8</math>.
 
- Number and percentage of participants with rSBA titers <math>\geq 128</math>.
 

Graphical display:	Reverse Cumulative Distribution plots will be produced to show the distribution of Day 29 rSBA titers, by serogroup and vaccine arm.

For a subset of participants, the following descriptive analysis will be conducted:

Endpoint:	Seroresponse in rSBA titers to meningococcal serogroups A, C, W, X and Y, from samples collected at Visit 3 (Study Day 29), where seroresponse is defined as a post-immunization (Day 29) rSBA titer of 32 or greater if the participant's pre-immunization (Baseline) rSBA titer was $< 8$ ; or a $\geq$ four-fold increase over baseline at Day 29 post-immunization if the participant's pre-immunization rSBA titer was $\geq 8$ .
Analysis Set:	Baseline Immunogenicity Analysis Set
Approach and reporting:	For each of the five serogroups (A, C, W, X, Y), the number and percentage of participants who show seroresponse in rSBA titers will be reported, by vaccine arm. Additionally, the Geometric Mean Fold Rise (GMFR) from baseline to Day 29 of rSBA titers to meningococcal

serogroups A, C, W, X and Y will be estimated, with 95% CI. The point and interval estimates will be obtained from a back transformation of the estimated mean difference of the log-transformed rSBA titers.

#### 8.4 Tertiary Immunogenicity Analysis

- Objective:** To assess the persistence of the immune responses at 6 months and 2 years after meningococcal vaccination.
- Endpoints:** rSBA titers against meningococcal serogroups A, C, W, X and Y, from samples collected at Visit 4 (Study Day 181, approximately 6 months after meningococcal vaccination) and Visit 5 (Study Day 730, approximately 2 years after meningococcal vaccination).
- Analysis Set:** Durability Immunogenicity Analysis Set
- Approach and reporting:** For each of the five serogroups (A, C, W, X, Y), descriptive summaries for rSBA titers at Day 181 and Day 730 will be tabulated by vaccine arm. These will include:
- Geometric Mean Titers (GMT), with 95% confidence intervals.
  - Range.
  - Number and percentage of participants with rSBA titers  $\geq 8$ .
  - Number and percentage of participants with rSBA titers  $\geq 128$ .
  - Geometric Mean Fold Rise (GMFR) from baseline, with 95% CI, for those participants in the Baseline Immunogenicity Analysis Set.

#### 8.5 Exploratory Immunogenicity Analysis

- Objective:** To compare the immune responses of the 9-month and 15-month group against each of the five meningococcal serogroups at Day 29.
- Endpoints:** rSBA titers against meningococcal serogroups A, C, W, X and Y, from samples collected at Visit 3 (Study Day 29).  
Seroprotective response at Study Day 29 to serogroups A, C, W, Y and X, with seroprotective response defined as serogroup specific rSBA antibody titers  $\geq 8$ .
- Analysis Set:** Analyses may include participants in the Per Protocol (PP) Analysis Sets and the mITT Analysis Sets.
- Approach:** The association of meningitis immune response 29 days post vaccination and age of meningitis vaccine administration will be explored through linear and/or logistic regression analyses (on the continuous log10 rSBA titers, or the seroprotective response binary endpoints, respectively). This approach will allow estimation of this association averaged across meningitis vaccines and meningitis serogroups, as well as adjustment for participants' characteristics and testing of potential effect modifiers.  
Being an exploratory objective/endpoint, the need for flexibility in the use of alternative or additional approaches is acknowledged.

## 8.6 Additional Immunogenicity Analysis

Although not specified in the protocol, additional summaries will be reported, to support assessment of the immune response to EPI scheduled vaccines concomitantly administered with NmCV-5 or MenACWY-TT. The endpoints include the Day 29 anti-measles IgG concentration, the anti-rubella IgG concentration, and the yellow fever neutralizing antibody titers. The analyses will be conducted in the Per Protocol Analysis Set. For each of the endpoints, descriptive summaries, including range and geometric mean titers with 95% confidence intervals, will be tabulated by vaccine arm.

## 9 SAFETY SECONDARY OBJECTIVES

### 9.1 Solicited Local and Systemic Adverse Events (Reactogenicity)

(Secondary) Endpoint: All solicited AEs reported during a 7-day follow-up period after meningococcal vaccination.

Per protocol, solicited injection site (local) and systemic reactogenicity adverse events are intended to be collected from time of study meningococcal vaccination through 7 days after each vaccination. Reactogenicity is intended to be first assessed about 30 minutes post-vaccination, then routinely assessed during the first four days post-vaccination and again on Day 8 Visit (Study Visit 2, scheduled at Day 8 with + 3-day window). For instances where there is reactogenicity of grade 2 or higher at the fourth day post-vaccination (Day 5), then daily assessments are intended to continue, until resolution or the severity of the reactogenicity is grade 1 (Mild). Severity grade for solicited AEs is recorded as none, mild, moderate, Severe and Potentially Life Threatening. Systemic AEs include Body temperature, Irritability, Drowsiness/Lethargy, Decrease Eating/Anorexia, Vomiting and Feverishness. Local AEs include erythema/redness (severity and largest diameter in cm), induration/swelling (severity grade and largest diameter in cm), and pain and/or tenderness.

For this safety endpoint, all reactogenicity symptoms reported after receipt of meningitis vaccination at Study Day 1 to Day 7 (including early assessment post-vaccination) will be included, as well as symptoms reported for Study Day 8, as long as the Day 8 assessment visit occurred within the specified visit window. Symptoms will be reported according to the Study Day for which they were reported in the Reactogenicity - Baseline and Early and Reactogenicity - Daily Log eCRFs.

Analysis Set: mITT Analysis Set

Approach: For each systemic and local solicited AE, the maximum severity reported by participants after vaccination, as collected in the Reactogenicity – Daily Log eCRF will be summarized. The number and percentage of subjects reporting each AE will be presented in tables by Symptom, Maximum Severity and vaccine arm. Additionally, the number and percentage of subjects reporting any Systemic Solicited Symptom, any Local Solicited Symptom will be calculated and reported by maximum Severity and vaccine arm. For calculation of percentages, the denominator is the number of subjects in the analysis set (excluding those missing all post-vaccination assessments for the symptom). For local AEs that report largest diameter, summary statistics (mean and SD, median and IQR, range) will be presented.

For each systemic and local solicited AE, bar plots describing the classification (proportion) of participants by the maximum severity of the AE reported, by Study Group, will be produced.

Additional Tables/Listings: All systemic and local solicited AEs will be summarized at the event level, by collection time (Day 1 early assessment and Days 1-8 post-vaccination), Symptom, Severity. For calculation of percentages, the denominator is the number of subjects in the analysis set (excluding those missing assessments for the day and symptom). Summary statistics for largest diameter of local AEs, as appropriate, will also be reported.

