Reactogenicity assessments will include an assessment of solicited AEs occurring from the time of each study meningitis vaccination through Day 8 after study vaccination with a meningococcal vaccine, which includes an assessment of meningitis vaccine injection site reactions including erythema (redness), swelling, and pain, as well as systemic reactions including fever, feverishness, irritability, decrease eating, vomiting, and drowsiness. Pre-administration reactogenicity assessments will be performed prior to each study meningitis vaccination to establish baseline, then the study vaccination will be given.

Parents/guardians, with the help of study field workers, will complete a subject memory aid from the time of study vaccination through at least 4 days. Subject memory aids will be reviewed by study staff for AEs (solicited injection site and systemic reactions and unsolicited AEs) at the clinic Visit 2 (Day 8).

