7 ASSESSMENT OF SAFETY

7.1 Assessing and Recording Safety Parameters

7.1.1 Adverse Events (AEs)

Adverse Event (AE): ICH E6 GCP defines an AE as any untoward medical occurrence in a patient or clinical investigation subject administered a pharmaceutical product regardless of its causal relationship to the study treatment. An AE can therefore be any unfavorable and unintended sign (including an abnormal laboratory finding), symptom, or disease temporally associated with the use of a medicinal (investigational) product. The occurrence of an AE may come to the attention of study staff members during study visits (including field visits) and interviews of a study recipient presenting for medical care, or upon review by a study monitor.

AEs, including solicited injection site and systemic (subjective and quantitative) reactions, not meeting the protocol-defined criteria for SAEs, will be recorded on the appropriate data collection form (DCF) or entered into the eCRF. Information to be collected for unsolicited non-serious AEs includes event description, date of onset, licensed study physician's assessment of severity and relationship to study product or alternate etiology (if not related to study product), date of resolution, seriousness, and outcome. AEs occurring during the trial-collection and reporting period will be documented appropriately regardless of relationship to study product. AEs will be followed through resolution.

Any medical condition that is present at the time that the subject is screened will be considered as baseline and not reported as an AE. However, if the severity of any pre-existing medical condition increases, it will be recorded as an AE. The time of reference for the AE is to be the time from receipt of the randomized blinded meningococcal vaccine.

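### SAP 9.1 summarises solicited symptoms after vaccination without using the pre-vaccination assessment, so mild systemic symptoms already present can inflate the absolute rates in both arms

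*SAP*

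**What the plan says.** Protocol 6.1 requires a reading before the injection: "Pre-administration reactogenicity assessments will be performed prior to each study meningitis vaccination to establish baseline". SAP 9.1 names the source forms when it says that symptoms are assigned to the study day for which they were "reported in the Reactogenicity - Baseline and Early and Reactogenicity - Daily Log eCRFs". The title of the first form suggests that it holds the pre-vaccination reading.

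The SAP 9.1 analysis rules refer only to the period after the injection:

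- Inclusion: "all reactogenicity symptoms reported after receipt of meningitis vaccination at Study Day 1 to Day 7 (including early assessment post-vaccination) will be included", plus Day 8 if that visit fell within its window.
- Summary measure: "the maximum severity reported by participants after vaccination, as collected in the Reactogenicity – Daily Log eCRF will be summarized".
- Percentages: "the denominator is the number of subjects in the analysis set (excluding those missing all post-vaccination assessments for the symptom").
- Event-level table: "by collection time (Day 1 early assessment and Days 1-8 post-vaccination), Symptom, Severity".

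Protocol 7.1.1 places solicited reactions among AEs and gives a general rule on conditions that pre-date the trial: "Any medical condition that is present at the time that the subject is screened will be considered as baseline and not reported as an AE". It then adds: "However, if the severity of any pre-existing medical condition increases, it will be recorded as an AE".

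**The concern.** The protocol collects a baseline for reactogenicity, but no analysis in the SAP uses it. Read literally, SAP 9.1 counts an infant who was mildly irritable or eating poorly before the injection, and no different the next day, as having a mild systemic solicited AE.

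Unsolicited events are treated differently. SAP 9.2 and 9.3 work from the date of onset, and their listings flag whether an event is a worsening of a baseline condition. Solicited events have no equivalent rule.

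What is at stake is the meaning of the absolute rates. Without a comparison with baseline, the systemic tables mix new reactions with symptoms that were already there. Those rates are the main output of a descriptive safety analysis, and under SAP 3.1 they go into the reports intended for WHO.

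**Working it through.** **Text check.** The documents state no figure that could be reproduced, so the first step is to follow the pre-vaccination reading through the SAP.

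1. Collection: required by Protocol 6.1.
2. Baseline tables: SAP section 7 covers demographics, anthropometry and vital signs, baseline rSBA, medical history, physical examination and concomitant medication. It does not cover baseline reactogenicity.
3. Endpoint: the SAP 9.1 inclusion rule, maximum severity and denominator all depend on post-vaccination assessments alone.
4. Event-level table: its first time point is the Day 1 early assessment, after the injection.
5. Protocol 9.6 does not mention baseline reactogenicity either.

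The reading is therefore taken and then not used.

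**Which symptoms can be affected.** SAP 3.3.5 shows that the form asks whether vaccine-related erythema or induration is visible, so attribution is part of the collection of those two signs. No such wording is shown for systemic symptoms. Protocol 4.1.2 excludes infants with fever of 37.5°C or more, or with moderate or severe acute infection, in the preceding 3 days. What remains is mainly mild, non-febrile irritability, drowsiness, reduced eating and vomiting.

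**Illustration of size.** Let r be the rate of new-onset systemic symptoms. Let b be the share of infants with a systemic symptom before the injection that is still reported afterwards. If the two are independent,

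reported rate = 1 − (1 − r)(1 − b).

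For r, take two of the phase 2 systemic solicited rates in Protocol 1.1.2: 3.9% (non-adjuvanted NmCV-5) and 5.4% (control). They serve only as plausible low rates, since the phase 2 control was a different vaccine and the children were 12 to 16 months old. The documents give no value for b, so 0% to 5% is assumed.

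Example for r = 3.9%, b = 1%: 1 − 0.961 × 0.99 = 0.0486.

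| b (assumed) | Reported, r = 3.9% | of 400 | Reported, r = 5.4% | of 200 | Difference (points) |
|---|---|---|---|---|---|
| 0% | 3.90% | 15.6 | 5.40% | 10.8 | −1.50 |
| 1% | 4.86% | 19.4 | 6.35% | 12.7 | −1.485 |
| 3% | 6.78% | 27.1 | 8.24% | 16.5 | −1.455 |
| 5% | 8.71% | 34.8 | 10.13% | 20.3 | −1.425 |

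The difference between arms equals (1 − b) × (3.9 − 5.4) points, so it shrinks only by the factor 1 − b. The ratio of the two rates moves more: 5.40/3.90 = 1.38 falls to 1.31, 1.21 and 1.16 at b = 1%, 3% and 5%. No planned safety analysis reports a ratio.

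**The case against.** Four objections deserve an answer.

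- **The SAP never says that pre-existing symptoms count.** This is correct, and a reader should not infer that it does. The endpoint is worded as solicited AEs, and site staff who apply Protocol 7.1.1 might leave a stable symptom out of the daily log. The documents do not show whether they do. But the inclusion rule is unqualified, and a programmer following it would count whatever had been recorded. If practice varied between staff, a written rule is needed all the more.
- **There is no contradiction with the protocol.** A reader might infer that SAP 9.1 breaches the AE definition in Protocol 7.1.1. The documents do not support that. The rule concerns a medical condition present at screening, which for Group 2 is some 3 to 6 months before vaccination (SAP section 7). A symptom that began after screening but before the injection is outside it. That also means the rule does not close the gap: only the pre-injection reading identifies such a symptom.
- **The 30-minute reading may not enter the main table.** SAP 9.1 includes the early assessment in the endpoint, yet takes maximum severity from the Daily Log, while the early assessment appears to sit on the other form. The point therefore rests on symptoms that persist into the daily log.
- **The effect is limited.** Infants must be in good health, and the exclusions remove febrile or more serious illness. Safety is descriptive with no hypothesis tests (Protocol 9.2), and any error overstates symptoms in both arms. All of this stands, and it limits how much weight the point can bear.

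**Conclusion.** The point holds as a gap in the analysis of solicited systemic symptoms. SAP 9.1 makes no use of a baseline that the protocol requires, so mild symptoms present before the injection can be reported as solicited AEs and can raise the absolute rates in both arms.

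The size cannot be determined from the documents. Under the assumed 1% to 5% background, independent of true reactions, a 3.9% rate would be reported as 4.9% to 8.7%. These figures show sensitivity and are not a forecast.

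Two stronger conclusions are tempting and unsupported. One is that a difference between the vaccines would be hidden: Step 2 randomisation balances pre-existing symptoms on average, and in the illustration the difference moves by less than 0.1 percentage point (from −1.50 to −1.43). The other is that local rates are similarly inflated: erythema and induration are asked about as vaccine-related, and injection-site tenderness presupposes an injection.

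No primary or secondary hypothesis test is affected. This is a cheap improvement.

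**What to change.** In SAP 9.1:

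1. Tabulate the pre-vaccination reactogenicity assessment by symptom, grade and arm, as its own column.
2. For systemic symptoms, add maximum-severity and any-systemic tables in which a symptom counts only if it was absent before vaccination or rose in grade afterwards.
3. Present these beside the existing all-symptoms tables, which stay as they are.

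SAP 3.1 asks for changes or additions to be documented and reported as post-hoc. If a WHO report has already been run, the new tables need that label.

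The cost is SAP wording and one extra derivation. It assumes that the pre-vaccination form recorded a grade for each systemic symptom, which should be checked first because its fields are not shown. The downside is that new-or-worsened rates will differ from those of trials that ignore baseline. The retained all-symptoms tables cover that comparison.
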